The high-risk non-cardiac surgical population represents a major global healthcare challenge. Recent estimates suggest that 234 million major surgical procedures are performed worldwide each year [1]. Complications following major surgery are a leading cause of morbidity and mortality [2-7]. Sickness absence to undergo surgery is second only to cardiovascular disease in terms of associated long-term mortality [2]. In the overall population, the incidence of post-operative complications and death is low. However, studies from the UK suggest a readily identified high-risk sub-group accounts for over 80% of post-operative deaths but less than 15% of in-patient procedures [5, 6]. In the UK, 170,000 patients undergo high-risk non-cardiac surgery each year [5, 6]. Of these patients, 100,000 will develop significant complications resulting in over 25,000 deaths [5-7]. Advanced age, co-morbid disease, major and urgent surgery are the key factors associated with increased risk [5-7]. This pattern of poor outcomes following major surgery can be readily identified worldwide [2-10]. Patients who develop complications but survive will still suffer reductions in functional independence and a substantial decrease in medium and long-term survival [2-4]. A prospective 13 year observational study of the Whitehall II cohort of 6478 British civil servants aged 35-55 examined the link between diagnoses associated with medical absence from work and long term all-cause mortality [2]. Physician-certified sickness absence attributable to undergoing a surgical operation was associated with a two-fold increased risk of mortality. Apart from circulatory disease, surgery was associated with the highest risk of later death compared to psychiatric, infectious, and respiratory disease. Despite strong evidence of the impact of poor surgical outcomes, our understanding of standards of care for patients undergoing major surgery is limited. In particular, little is known about the availability of critical care resources for non-cardiac surgical patients and the impact of critical care admission on clinical outcomes. Importantly, survival amongst patients who develop postoperative complications varies widely between hospitals, confirming both the potential and the need to improve clinical outcomes in this population [11].

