Little is known about standards of care for patients undergoing major non-cardiac surgery across Europe or clinical outcomes following such procedures. It has been suggested by some that poor surgical outcomes may vary between nations but this belief may simply reflect better recognition of the issue. Evidence from sources across the developed world suggests the existence of a large population of patients who can be readily identified as being at high risk of post-operative complications and death [2-10]. There is increasing recognition of the massive potential impact of even small improvements in peri-operative care [17, 18]. However, significant policy change can only be driven by robust and powerful data. Mismatch between critical care resource provision and peri-operative risk may be widespread or confined to a small number of nations. Either way, a rigorous evaluation of standards of peri-operative critical care across Europe would provide important data which could trigger a step-change in the current approach to care of the patient undergoing major non-cardiac surgery.

Research questions

1. What is the in-hospital mortality rate for patients undergoing non-cardiac surgery in Europe?
2. What is the duration of hospital stay for patients undergoing non-cardiac surgery in Europe?
3. What is the current standard of peri-operative critical care provision for patients undergoing non-cardiac surgery in Europe?
4. What is the current standard of haemodynamic (cardiac output) monitoring for patients undergoing non-cardiac surgery in Europe?
5. Is there any evidence of differences in the standard of peri-operative care provision for patients undergoing non-cardiac surgery in different health-care systems within Europe?
6. Is there any evidence of differences in hospital stay and mortality for patients undergoing major non-cardiac surgery in different health-care systems within Europe?
7. What factors determine planned and unplanned admission to critical care after surgery?
8. Are the factors associated with critical care admission similar to those associated with post-operative death?

Methods

Seven day, international cohort study of adult (≥ 16 years) patients undergoing in-patient non-cardiac surgery.

Inclusion criteria

Consecutive patients admitted to participating centres undergoing elective and non-elective non-cardiac surgery commencing during the seven day study period (00⁰⁰ day 1 to 24⁰⁰ day 7) with a planned overnight stay.

Exclusion criteria

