Patients undergoing planned day-case surgery, cardio-thoracic surgery, neurosurgery, radiological or obstetric procedures.

Centres

We aim to recruit as many European centres as possible. We anticipate that a minimum of 150 hundred centres in ten or more nations will be required. We are hopeful that we can meet or exceed this target through the activities of national lead investigators and the support of key organisations such as the European Society of Intensive Care Medicine and the European Society of Anaesthesiology. Centres will receive an individual report allowing comparison of their dataset to that of their national cohort and of the overall dataset. We hope this will act as an incentive to participate.

Ethics approval

Ethics approval may not be required in all participating nations. National lead investigators will be responsible for clarifying the need for ethics approval and applying for this where appropriate. Centres will not be permitted to record data unless ethics approval or an equivalent waiver is in place. This study is in effect a large scale clinical audit. We expect that in most, if not every participating country, there will be no requirement for individual patient consent as all data will be anonymised and is already recorded as part of routine clinical care.

Data collection and collation

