- Respiratory arrest prior to critical care admission
- Cardiac arrest prior to critical care admission
- Component data for SAPS III score
- SOFA score (one of four scores in each of six domains)

Physiological data following 24 hours in critical care:

- SOFA score (one of four scores in each of six domains)
- Respiratory support (invasive or non-invasive)
- Renal replacement therapy (planned or unplanned)

Physiological data following 48 and 72 hours in critical care:

- SOFA score (one of four scores in each of six domains)
- Respiratory support (invasive or non-invasive)
- Renal replacement therapy (planned or unplanned)

Follow-up data for patients admitted to critical care:

- Critical care discharge: Date and time
- SOFA score in last 24 hours of ICU stay (for patients staying ≥ 96 hours)
- Major therapeutic limitation during ICU stay (Y / N, date)
- Critical care discharge: planned or unplanned
- Critical care mortality

Sample size calculation

We anticipate that approximately 20,000 patients will be required to provide a sample of up to 2,000 admissions to critical care after surgery. Assuming an overall mortality rate following surgery of 1%, a sample size of 20,000 patients will yield 200 deaths. This will allow the inclusion of at least fifteen variables in a logistic regression model for mortality. The rate of admission to critical care is likely to vary between nations but an overall rate of 10% (either planned or unplanned) will yield data on 2000 admissions to critical care, whilst an overall rate of 5% will yield 1000 admissions. We expect this to allow a robust logistic regression model for this outcome. 20,000 patients will also provide >99% confidence for the overall mortality rate with 0.37% confidence width. This dataset would also have sufficient generalisability to inform the practice of peri-operative care on an international basis. If 200 deaths are observed in an overall sample of 20,000 patients, the 99% confidence interval for the proportion would be (0.0083 - 0.0120) with a confidence width of 0.37%. This dataset would also have sufficient generalisability to inform the practice of peri-operative care on an international basis.

Statistical analysis

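### The 99% interval for overall mortality (width 0.37 points) is computed correctly but assumes independent patients, which the protocol does not say and which its centre-based sampling does not support

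*Protocol*

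**What the plan says.** All the figures are in the protocol's section on sample size calculation.

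- **Planning rate and yield:** "Assuming an overall mortality rate following surgery of 1"%, "a sample size of 20,000 patients will yield 200 deaths".
- **Precision as a promise:** "20,000 patients will also provide >99% confidence for the overall mortality rate with 0.37% confidence width".
- **Precision as a conditional statement:** "If 200 deaths are observed in an overall sample of 20,000 patients", then "the 99% confidence interval for the proportion would be (0.0083 - 0.0120) with a confidence width of 0.37"%.

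The section mentions no design effect, no intraclass correlation and no independence assumption. The only intraclass correlation in the protocol is under Dataset, where it concerns the reliability of data collection.

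The sampling is described elsewhere. The inclusion criteria take consecutive eligible patients in participating centres over seven days. Under Centres the protocol says "We anticipate that a minimum of 150 hundred centres in ten or more nations will be required"; the number is garbled, and I read it as 150. The target is set by research question 1: "What is the in-hospital mortality rate for patients undergoing non-cardiac surgery in Europe". The sample size section also claims, twice, that the data will generalise internationally. The opening background notes that "survival amongst patients who develop postoperative complications varies widely between hospitals", and research question 6 asks whether mortality differs between health-care systems.

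**The concern.** A binomial interval counts 20,000 separate pieces of information. Here patients arrive in blocks: every eligible patient in a centre for a week, with centres grouped in nations. If hospitals differ in their underlying mortality, patients from the same hospital resemble each other, and the pooled rate has an extra variance component that shrinks with the number of hospitals, not the number of patients. The stated width sets that component to zero without saying so.

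This is the only precision figure the protocol gives for its primary outcome, in-hospital mortality, and it is worded as something the sample will provide. A reader would take 0.37 points as the expected precision of the European mortality estimate. If an interval were also computed this way at the end, it would be called a 99% interval but would cover less often than that.

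**Working it through.** **Inputs from the protocol:** n = 20,000; 200 deaths; p = 0.01; two-sided 99%, so z = 2.576; at least 150 centres (my reading of the garbled number) and at least ten nations. With equal centres, m = 20,000/150 = 133.3 patients per centre.

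**Assumed, because the documents give no figure:** coefficient of variation (CV) of true mortality between hospitals, 30% to 60%; between nations, 20% to 30%; equal cluster sizes.

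**Step 1. Reproduce the stated figure.** The exact (Clopper-Pearson) 99% interval for 200/20,000 is 0.00828 to 0.01196, width 0.368 points. This matches the protocol. Other binomial methods give nearly the same width: Wald 0.362, Wilson 0.364. All assume independent patients.

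**Step 2. Variance under independence.** p(1 − p)/n = 0.01 × 0.99/20,000 = 4.95 × 10⁻⁷. Wald width = 2 × 2.576 × √(4.95 × 10⁻⁷) = 0.362 points. This is the like-for-like base for the steps below.

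**Step 3. Add hospitals.** Added variance = (CV × 0.01)²/150.

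- CV 30%: 0.003²/150 = 0.60 × 10⁻⁷. Variance ratio 5.55/4.95 = 1.12; width 0.362 × √1.12 = 0.38.
- CV 60%: 0.006²/150 = 2.40 × 10⁻⁷. Variance ratio 7.35/4.95 = 1.48; width 0.362 × √1.48 = 0.44.

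Coverage of the nominal 99% binomial interval is 2Φ(2.576/√ratio) − 1, which gives 98.5% and 96.5%. Applying the same factors to the exact width of 0.368 gives 0.39 and 0.45, so the choice of binomial method hardly matters.

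**Step 4. Cross-check by intraclass correlation (ICC).** The ICC implied by a CV is CV² × p/(1 − p): 0.0009 for 30% and 0.0036 for 60%. The design effect, 1 + (m − 1) × ICC, is 1 + 132.3 × 0.0009 = 1.12 and 1 + 132.3 × 0.0036 = 1.48, in agreement with Step 3. For larger assumed ICCs of 0.005 and 0.01, the design effects are 1.66 and 2.32 and the Wald widths 0.47 and 0.55. Unequal centres widen the interval further: with a CV of centre size of 0.7 and an ICC of 0.005, the width is 0.51 instead of 0.47.

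**Step 5. Sensitivity: nations as a sample too.** Added variance = (CV × 0.01)²/10, which is 4.0 × 10⁻⁷ at 20% and 9.0 × 10⁻⁷ at 30%. With 20 nations and 300 centres, all the added terms halve.

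| Centres / nations | Hospital CV | Nation CV | Variance ratio | Width (points) | Coverage |
|---|---|---|---|---|---|
| 150 / nations fixed | 30% | none | 1.12 | 0.38 | 98.5% |
| 150 / nations fixed | 60% | none | 1.48 | 0.44 | 96.5% |
| 150 / 10 | 30% | 20% | 1.93 | 0.50 | 94% |
| 150 / 10 | 60% | 30% | 3.30 | 0.66 | 84% |
| 300 / 20 | 30% | 20% | 1.46 | 0.44 | 97% |
| 300 / 20 | 60% | 30% | 2.15 | 0.53 | 92% |

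These rows use the normal quantile.

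**The case against.** **The calculation is correct, and one of the two sentences is conditional.** This stands. A reader might infer a calculation error; there is none. The defect is that the condition behind the figure is not stated.

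**The protocol does not assert that its primary outcome varies between hospitals.** This also stands. The background remark concerns survival among patients who already have a complication, not in-hospital mortality among all surgical patients. Research question 6 only asks whether systems differ, and the background allows that apparent national differences may reflect better recognition of the problem. These passages make clustering plausible but do not measure it.

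**For the participating hospitals taken as fixed, a binomial interval is adequate.** True, but research question 1 asks about Europe and the sample size section claims international generalisability. For that target the hospitals are a sample.

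**Nations need not be a random sample.** This stands in large part. The protocol recruits as many European centres as it can, and treating nations as fixed strata is legitimate; no between-nation term then enters. Every width of 0.50 points or more in the table depends on the other choice, so a reader should not take those as the expected widths.

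**150 centres and ten nations are minimums.** They are, and the protocol hopes to exceed them. The 300/20 rows show that the gap shrinks but does not close.

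**The analysis method can be left to a statistical analysis plan.** Yes, and none is shown. The protocol does not say how the final mortality interval will be computed, so it cannot be said that the analysis will ignore clustering. A better analysis would still not make the stated width what the design is expected to deliver.

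**The sample size does not rest on this width.** Also true. The 20,000 is justified first by critical care admissions and by 200 deaths for regression; precision is an addition and no target width is set. The documents do not support reading this as a case for more patients.

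**Conclusion.** The point holds as an unstated independence assumption. The direction is firm: any positive between-hospital variation makes the true width larger than the binomial one and the coverage of a simple binomial interval lower than 99%. The size is not firm, because every figure beyond the reproduced interval rests on an assumed CV or ICC.

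With hospitals alone, the loss is modest: 0.38 to 0.44 points against 0.37. It becomes material only with stronger hospital variation, with very unequal centres, or if nations are treated as a sample. The phrase about more than 99% confidence is a separate small slip, since the interval the protocol gives is a 99% interval. Overall the point is minor to moderate, and it touches neither the planning rate nor the number of patients.

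**What to change.** In the section on sample size calculation:

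1. Label 0.37 points as the width if patients are independent.
2. Add the width under a stated assumption about between-hospital variation, for example 0.38 to 0.44 points for a CV of 30% to 60% with 150 equal centres. As a sensitivity, add the width with between-nation variation.
3. Replace the wording about more than 99% confidence with a plain reference to a 99% confidence interval.
4. State, in the protocol or the statistical analysis plan, that the interval for overall mortality will allow for clustering by centre, for example with a cluster-robust or hierarchical variance.

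The cost is a few sentences and a less favourable stated precision. No extra patients, data or design changes are needed.

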The data to be collected are all collected as part of routine clinical care. Categorical variables will be described as proportions and will be compared using chi-square or Fisher's exact test. Continuous variable will be described as mean and standard deviation if normally distributed or median and inter-quartile range if not normally distributed. Comparisons of continuous variables will be performed using one-way ANOVA or Mann-Whitney test as appropriate. Uni-variate analysis will be performed to test factors associated with planned and unplanned admission to critical care and / or in-hospital death. A multiple logistic regression model will be used to identify independent risk factors. A stepwise approach will be used to enter new terms into the logistic regression model where $p < 0.05$ was set as the

limit for inclusion of new terms. A logistic regression model will be performed to assess independent association between prognostic factors and outcomes. Results of logistic regression will be reported as adjusted odds ratios (OR) with 95% confidence intervals. A single final analysis is planned at the end of the study.

Primary outcome measure

- In-hospital mortality

Secondary outcome measures

- Duration of hospital stay
- Planned admission to critical care
- Unplanned admission to critical care
- Duration of critical care stay

Organisation

Subject to funding approval, it is proposed that the EuSOS study will be conducted by the EuSOS study group on behalf of the European Society of Intensive Care Medicine and the European Society of Anaesthesiology. The steering committee will be chaired by RP. The study management team will be appointed by the steering committee and led by RP. The duties of this team will include administration of all project tasks, communication between project partners (including funders, steering committee members, national and local co-ordinators, etc), data collation and management and preparation of reports for individual study sites. The Steering committee is responsible for the scientific conduct and consistency of the project. The Steering committee will ensure communication between the funder(s), study management team and co-ordinators as necessary.

National co-ordinators

National co-ordinators will be appointed by the steering committee to lead the project within individual nations and:

- Identify local co-ordinators in participating hospitals
- Assist with translation of study paperwork as required

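### The only comparison of cardiac output monitoring between health-care systems that the protocol states is unadjusted, so differences in case mix can pass for, or hide, differences in practice

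*Protocol*

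**What the plan says.** Two research questions are involved. Question 4 is descriptive: "What is the current standard of haemodynamic (cardiac output) monitoring for patients undergoing non-cardiac surgery in Europe". Question 5 is comparative: "Is there any evidence of differences in the standard of peri-operative care provision for patients undergoing non-cardiac surgery in different health-care systems within Europe". Neither is limited to major surgery, whereas question 6 is: "Is there any evidence of differences in hospital stay and mortality for patients undergoing major non-cardiac surgery in different health-care systems within Europe".

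The Inclusion criteria define a broad cohort: "Consecutive patients admitted to participating centres undergoing elective and non-elective non-cardiac surgery commencing during the seven day study period". Form B in the Dataset section records grade of surgery in three levels, together with urgency, procedure category, ASA grade, age and cardiac output monitoring.

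The Statistical analysis section gives a general rule for categorical data: "Categorical variables will be described as proportions and will be compared using chi-square or" Fisher's exact test. It then says where its risk-factor work is aimed: "Uni-variate analysis will be performed to test factors associated with planned and unplanned admission to critical care and / or in-hospital death". Multiple logistic regression with stepwise entry follows, and a further sentence promises a logistic model relating prognostic factors to outcomes, reported as adjusted odds ratios. The outcome measures are in-hospital death, hospital stay, planned and unplanned critical care admission, and critical care stay. Monitoring is not among them. Neither nation nor health-care system is named as a model term.

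**The concern.** A crude proportion of patients monitored combines two things: how often the device is used for a given type of operation, and how many operations of each type a system entered in the study week. Question 5 concerns the first. An unadjusted test over all in-patients responds to both.

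The Appendix shows how wide the range of surgery is. Minor includes small biopsies, Intermediate includes cataract surgery, and Major includes aortic aneurysm repair and major gut resection. It also defines the monitor to include the pulmonary artery catheter and oesophageal Doppler. It is reasonable, though not stated in the protocol, to expect use to differ across these grades. The Centres section aims for as many centres as possible, and nothing in it balances case mix between nations.

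At stake is the reading of a between-system difference as a difference in standard of care, in a study that hopes to influence policy.

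**Working it through.** **The plan's own figure.** The protocol gives no precision or power figure for comparisons between systems. Its one precision statement is the 99% interval for 200 deaths in 20,000 patients, 0.0083 to 0.0120 with width 0.37%. The exact (Clopper-Pearson) method gives 0.00828 to 0.01196, width 0.368%, so it reproduces. It has no bearing on question 5.

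**Inputs from the protocol.** 20,000 patients (Sample size calculation) and ten or more nations (Centres), so about 20,000 / 10 = 2,000 per nation if spread evenly.

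**Inputs assumed, because the protocol gives none.** Use of monitoring in major surgery (*m*) and in other surgery (*o*), identical in both systems; the share of major surgery in each system (*s*); patients independent of each other.

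**Formulas.**
- Crude use: p = s·m + (1 − s)·o
- Crude test with n per system: z = |p₂ − p₁| / √(2·p̄(1 − p̄)/n), where p̄ is the mean of p₁ and p₂
- Chance of p < 0.05: Φ(z − 1.96) + Φ(−z − 1.96)

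**Strong gradient (m = 10%, o = 1%), shares 30% and 40%, n = 2,000.**
- p₁ = 0.30×0.10 + 0.70×0.01 = 0.037
- p₂ = 0.40×0.10 + 0.60×0.01 = 0.046
- z = 0.009 / √(2×0.0415×0.9585/2,000) = 0.009 / 0.00631 = 1.43
- False rejection ≈ Φ(−0.53) ≈ 0.30; simulation of 20,000 datasets gives 0.29

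**Strong gradient, shares 30% and 50%.**
- p₂ = 0.50×0.10 + 0.50×0.01 = 0.055
- z = 0.018 / 0.00662 = 2.72
- False rejection ≈ Φ(0.76) ≈ 0.78, as in the simulation

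**Weak gradient (m = 5%, o = 3%), shares 30% and 40%.**
- p₁ = 0.015 + 0.021 = 0.036; p₂ = 0.020 + 0.018 = 0.038
- z = 0.002 / 0.00597 = 0.34
- False rejection ≈ 0.05 counting the near tail only, 0.06 counting both

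**False rejection by the crude test, identical practice in both systems** (first three rows simulated, last row by the formula with both tails):

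| Use, major / other | Major share | Crude use | n = 1,000 | n = 2,000 | n = 10,000 |
|---|---|---|---|---|---|
| 10% / 1% | 30% v 35% | 3.7% v 4.15% | 8% | 11% | 38% |
| 10% / 1% | 30% v 40% | 3.7% v 4.6% | 17% | 29% | 89% |
| 10% / 1% | 30% v 50% | 3.7% v 5.5% | 49% | 78% | 100% |
| 5% / 3% | 30% v 40% | 3.6% v 3.8% | 6% | 6% | 12% |

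The bias does not shrink with sample size, so a larger study makes a false positive more likely.

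**Stratifying by grade.** In the simulated scenarios with the strong gradient, a Mantel-Haenszel test stratified by grade rejected in 4.7% to 5.1% of datasets, close to the nominal 5%.

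**Masking.** Let system A use the monitor in 10% / 1% with a 30% major share: 3.7% crude. Let system B use it in 6% / 0.6% with a 50% major share: 0.030 + 0.003 = 3.3% crude. Within each grade, B's use is 0.6 times A's, but the crude ratio is 3.3 / 3.7 = 0.89. At 2,000 per system, z = 0.004 / 0.00581 = 0.69, p ≈ 0.49.

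**The case against.** The best reply is that the chi-square sentence is a general convention. It does not mention monitoring, nations or health-care systems, and the protocol nowhere says that a crude test is the whole analysis of question 5. A later sentence promises adjusted odds ratios for outcomes in general terms, and an analysis plan that was not available here may add adjustment. This stands in part: that no adjusted analysis is intended is something a reader might infer, and the text does not say it. But the section is not merely silent. It gives a test for categorical variables and aims its univariate step at "factors associated with planned and unplanned admission to critical care and / or in-hospital death". For monitoring, the stated test is the unadjusted one.

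Four stronger readings are tempting, and the protocol does not support them.

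- **That all care standards are compared only crudely.** Critical care provision is the care standard on which the background and question 3 centre. Planned and unplanned admission are listed outcomes with a planned logistic model, which the Sample size calculation also discusses.
- **That systems will appear to differ.** The effect depends on the gradient, the case-mix gap and the numbers, none of which the protocol gives. With shares of 30% and 40% and 2,000 per system, most datasets show no significant difference even under the tenfold gradient.
- **That checklist use suffers in the same way.** Nothing in the protocol suggests that it varies with grade of surgery.
- **That the overall proportion is the wrong answer to question 4.** That question is worded for all non-cardiac surgery, and the overall proportion answers it.

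**Conclusion.** The point holds for cardiac output monitoring under question 5. The stated comparison is unadjusted, in a cohort of all grades of surgery, and cannot separate practice from case mix. At 2,000 patients per system, false rejection runs from about 5% to 6% with a weak gradient, through about 29% (shares 30% and 40%), to about 78% (shares 30% and 50%) with a tenfold gradient.

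These figures rest on assumed rates and shares and on independent patients, so they show what can happen and do not forecast it. The independence assumption also matters for the remedy: if use varies between centres within a system, adjusting for case mix alone would not bring the error rate to its nominal level. The primary outcome and the critical care admission analyses are not affected by this point.

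**What to change.** Add to the Statistical analysis section:

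- **Question 5.** Monitoring will be compared between systems with a logistic model containing nation or health-care system, with age, ASA grade, procedure category, grade and urgency of surgery as forced terms (not subject to stepwise entry), allowing for clustering by centre. Proportions standardised to the pooled case mix, with intervals that allow for clustering, are an acceptable alternative. The crude chi-square or Fisher's exact comparison is kept as description.
- **Question 4.** Keep the overall proportion and also report it by grade and urgency of surgery.

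The cost is one more regression and a table. Every covariate is already on Form B and centre is coded for each patient, so no new data are needed. Intervals for differences between systems will be somewhat wider once clustering is allowed for.

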- V A patient who is not expected to survive for 24 hours without the operation

Duration of surgery

Time in minutes from induction of anaesthesia to patient leaving the operating room

Post-anaesthetic recovery unit

A post-anaesthetic recovery unit is dedicated facility for the care of all patients following surgery under anaesthesia. This does not include units which routinely care for invasively ventilated patients overnight. Duration of stay is the time from arrival to departure measured in minutes.

Post-operative Critical Care

For this study, a critical care unit is defined as a facility routinely capable of admitting patients who require invasive ventilation overnight. This differs from a post-anaesthetic recovery unit which has a primary purpose to provide care for all patients after anaesthesia regardless of dependency. Duration of stay is the time from arrival to departure measured in hours (part hours to count as one whole hour).

Duration of hospital stay

Time in days from the day of surgery to the day the patient leaves hospital. This will not be adjusted for delays relating to provision of social care in the community.

Haemodynamic (cardiac output) monitor

Any technology which provides a measurement of cardiac output. This would include oesophageal Doppler, pulmonary artery catheter and arterial waveform analysis but not devices which solely estimate arterial pressure variability.

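### The only methods named for comparing duration of stay are unadjusted, and the rank test is for two groups, so a difference between health-care systems could not be separated from case mix

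*Protocol*

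**What the plan says.** Item 6 of the protocol's research questions reads: "Is there any evidence of differences in hospital stay and mortality for patients undergoing major non-cardiac surgery in different health-care systems within Europe". On the number of nations, the Centres section says: "We anticipate that a minimum of 150 hundred centres in ten or more nations will be required" (the centre count is read here as 150, on the assumption of a typing slip).

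The secondary outcome measures include "Duration of hospital stay" and "Duration of critical care stay". The statistical analysis section gives one sentence on comparing such variables: "Comparisons of continuous variables will be performed using one-way ANOVA or Mann-Whitney test as appropriate". It ties the summary statistics to normality, with median and inter-quartile range for non-normal data. Its univariate risk-factor work is confined to other outcomes: "Uni-variate analysis will be performed to test factors associated with planned and unplanned admission to critical care and / or in-hospital death". The adjusted model that follows is logistic, reported as odds ratios.

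The appendix defines hospital stay as "Time in days from the day of surgery to the day the patient leaves hospital". For critical care it says: "Duration of stay is the time from arrival to departure measured in hours (part hours to count as one whole hour". Neither definition mentions death.

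**The concern.** Question 6 puts stay and mortality side by side, but the protocol treats them differently. Mortality gets an adjusted model and stay does not. Length of stay is bounded below and usually right-skewed, so the choice left open by the analysis sentence leans towards the rank test, and the rank test named cannot take more than two groups.

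The larger problem is attribution. Health-care systems will differ in who is operated on and for what. An unadjusted comparison mixes that difference with any difference in how care is delivered. With about 20,000 patients, modest imbalances in case mix can produce small p-values, and these could be reported as effects of the system. The variables needed to deal with this are on Form B, but the protocol links none of them to stay.

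**Working it through.** **The plan's own figures.** The protocol states no power or precision for stay. Its one precision figure concerns mortality and reproduces: the exact 99% interval for 200/20,000 is 0.00828 to 0.01196, width 0.368%, against the stated 0.0083 to 0.0120 and 0.37%.

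**Inputs from the protocol.** 20,000 patients; 1% mortality, so 200 deaths; 2,000 or 1,000 critical care admissions (10% or 5%); ten or more nations; 150 centres. Hence 20,000/10 = 2,000 patients per nation and 20,000/150 ≈ 133 per centre. All other inputs below are assumptions.

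**1. Which method serves which outcome.**
- One-way ANOVA: any number of groups, unadjusted.
- Mann-Whitney: two groups, unadjusted.
- Logistic regression: adjusted, but for a binary outcome. Stay would have to be dichotomised, and no cut-point is given.

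No stated method is both suited to a duration and adjusted.

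**2. Case mix.** If stay is the same within each stratum, the crude difference in means is (p2 − p1) × (difference in mean stay between strata).
- Assumed 40% v 20% in the longer-stay stratum, means of 6 and 2 days: 0.20 × 4 = 0.8 day.
- Simulation (400 runs, 2,000 per nation, lognormal stay rounded up to whole days, medians 4 and 2 days before rounding, log-scale SD 0.9):

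| Shares | Crude mean difference (days) | Mann-Whitney rejects | ANOVA rejects |
|---|---|---|---|
| 30% v 30% | 0.00 | 4.5% | 4.5% |
| 30% v 33% | 0.08 | 10% | 10% |
| 30% v 35% | 0.14 | 19% | 18% |
| 30% v 40% | 0.30 | 62% | 46% |

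The stratum was set up as major versus other surgery, but the arithmetic is the same for any binary factor with these stays.

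**3. Number of groups.** Ten nations give 10 × 9/2 = 45 pairs. If all pairs were tested at 5%, the family-wise error is P(studentised range > 1.96√2; k groups, infinite df) = 0.627 for k = 10 and 0.822 for k = 15. Simulated Mann-Whitney tests gave 0.62 for k = 10 (300 runs).

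**4. Clustering.** Design effect = 1 + (m − 1) × ICC with m = 20,000/150 = 133.3. An ICC of 0.01 gives 1 + 132.3 × 0.01 = 2.3, and 0.05 gives 1 + 132.3 × 0.05 = 7.6. The simulated type I error of a two-nation Mann-Whitney test at nominal 5% was 16% and 45%.

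**5. Deaths, if counted as ended stays.** Shift in mean = mortality × (day of death − survivors' mean). With a survivors' mean of 5 days and 1% mortality: 0.01 × (1 − 5) = −0.04 day if all die on day 1, and 0.01 × (15 − 5) = +0.10 day if all die on day 15. With all deaths on day 1, Mann-Whitney rejects in 12% of runs at mortality 0.5% v 2%, and in 33% at 1% v 4%. In critical care, deaths could make up at most 200/2,000 = 10% or 200/1,000 = 20% of stays, if every death occurred there.

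**The case against.** The best defence is that the analysis sentence is generic. It covers all continuous variables, does not forbid adjustment, and leaves detail to an analysis plan that is not at hand. The covariates are collected, and the adjusted model is said to concern outcomes in general. That the protocol leaves the door open is true. But it names specific methods, and none of those suited to a duration adjusts for anything.

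A reader might infer several stronger things that the protocol does not support:

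- *The plan cannot address question 6 for stay.* One-way ANOVA is an overall test for ten or more groups, and with about 2,000 patients per nation skewness alone does not invalidate a comparison of means. A crude difference can be detected. It cannot be attributed to the system.
- *Deaths are to be counted as completed stays.* The definitions are silent on death. Mortality is recorded both in hospital and in critical care, and an analysis plan could supply the rule. Nor is the direction fixed: early deaths shorten mean stay and late deaths lengthen it.
- *45 pairwise tests are planned.* Nothing says so. Question 6 refers to systems, whose number is not fixed, and the count of nations is a recruitment expectation. The 63% and 82% only show what follows if Mann-Whitney were stretched over all pairs.
- *Surgical grade will distort the answer to question 6.* That question is worded for major surgery. If it is restricted to that grade, imbalance between major and other surgery drops out. Age, ASA grade, procedure and urgency remain.

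**Conclusion.** The point holds in limited form. As the protocol stands, the stay half of question 6 would rest on crude comparisons that cannot be separated from case mix, and the only rank test named does not extend beyond two groups. This follows from the text and needs no assumed number.

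The size is illustrative only. Stay distributions, case-mix shares and ICCs are assumed throughout. On those assumptions, a 5 to 10 percentage-point imbalance in a factor that doubles stay produces a false signal in roughly 18% to 62% of two-nation comparisons, depending on the imbalance and the test. Ignoring clustering alone raises a nominal 5% error to about 16% to 45%.

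Death is a subsidiary matter. At 1% mortality its effect on mean hospital stay is small (−0.04 to +0.10 day in the example). It could be larger for critical care stay or where mortality differs between nations, but the protocol gives no critical care mortality from which to say how much. These are secondary outcomes, so the primary mortality result is not touched, but they serve a stated research question and the plan should be amended.

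**What to change.** In the statistical analysis section:

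1. Replace Mann-Whitney with Kruskal-Wallis for unadjusted comparisons of more than two groups, keeping Mann-Whitney for two.
2. Base the between-system comparison of hospital stay and critical care stay on a regression model adjusted for the same case-mix variables as mortality and allowing for clustering by hospital. Report the system effects from that model.
3. Have that model separate death from live discharge, since the appendix definitions do not. Time to live discharge with death as a competing event is one suitable form. Which competing-risk model to use is a matter of preference.

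The cost is revised wording and modest extra analysis. The covariates are already on Form B. The date of surgery is not among the Form B items listed, but the protocol's own definition of hospital stay already needs it, so it is not an added burden of this change.
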